**6.2 Subject/Parent Reimbursement**

The study will provide the Guardian RT and related supplies and the study HGM and test strips.

The study will be paying \$100 for the CRC admission and \$25 for the study enrollment visit to cover travel and other visit-related expenses. Payment will not be made for missed visits. Payment will be made after the child completes the study.

At the end of the study, subjects will be able to keep the study HGM.

**6.3 Subject Withdrawal**

Participation in the study is voluntary, and a subject may withdraw at any time. The investigator may withdraw a subject who is not complying with the protocol.

**6.4 Confidentiality**

For security purposes, subjects will be assigned an identifier that will be used instead of their name. Protected health information gathered for this study will be shared with the coordinating center, the Jaeb Center for Health Research in Tampa, FL. Information given to the coordinating center will include: diagnosis, general physical exam information (height/weight/blood pressure/etc.) insulin, questionnaire results, hemoglobin A1C results, continuous glucose monitor results, blood work results, HGM blood glucose measurements, information pertaining to hypoglycemic excursions and the treatment given, as well as all other study related data gathered during study visits. During the CRC admission, the Guardian-RT, study HGM and subject's insulin pump (if downloadable) will be downloaded to a computer that is secured and password protected, the files will be sent directly to the coordinating center via email. All files will include only the subject's identifier; no names or personal information will be included. Laboratory specimens will be sent to the University of Minnesota which serves as the central lab for DirecNet. Specimens may also be sent to other laboratories.

861  
862 During the study, subjects will be asked to wear the Guardian RT and use the study HGM which  
863 will be downloaded by the study personnel at the end of the CRC admission. The downloaded data  
864 will be emailed to the coordinating center. No names or personal information will be included.  
865 LifeScan Inc., the company providing the study HGMs and test strips for the study will be provided  
866 with the downloaded data from the study HGM. The data provided to LifeScan Inc. will include  
867 only the subject's identifier; no names or personal information will be included.

868  
869  
870  
871  
872  
873  
874  
875  
876  
877  
878  
879  
880  
881  
882  
883  
884  
885  
886  
887  
888  
889  
890  
891  
892  
893  
894  
895  
896  
897  
898  
899  
900  
901  
902  
903  
904  
905  
906  
907  
908  
909  
910  
911  
912  
913  
914  
915  
916  
917

## Chapter 7 Statistical Considerations

A detailed statistical analysis plan will be written and finalized prior to the completion of the study. The analysis plan synopsis in section 7.2 contains the framework of the anticipated final analysis plan, which will supersede section 7.2 when it is finalized.

### 7.1 Sample Size

Jones et al. (9) measured hormone levels in children with type 1 diabetes during induced hypoglycemia. The standard deviation (calculated by multiplying their reported standard error by the square root of the sample size and dividing by 5.46 to convert to pg/mL) for epinephrine was 306 pg/mL. With this standard deviation and a two-tailed test with type I error rate of 5%, a sample size of 50 subjects (25 in each age group) will give approximately 92% power to detect a mean difference of 300 pg/mL between the two age groups.

After N=30 subjects have completed the subcutaneous insulin infusion test an interim analysis will be performed to re-evaluate the sample size calculation above. The standard error for the age effect from the ANCOVA model for epinephrine described in section 7.2.1.1 will be calculated using the outcome data from the first 30 subjects. This will be used to update the calculation above to obtain the sample size necessary to detect a mean difference of 300 pg/mL with 90% power. Results will be presented to the DirecNet DSMB to determine whether the study should be stopped for either efficacy/futility or whether recruitment should continue to the newly calculated sample size (up to a maximum of 50 total subjects).

To avoid inflating the type I error rate with this interim analysis, the following stopping guidelines will be recommended: If N=30 subjects provides  $\geq 80\%$  power using the updated variance estimate or if N=50 would only increase this power by  $< 5\%$ , then no additional subjects will be recruited and statistical analysis will proceed without adjustment for alpha spending. Otherwise, Pocock's test will be used to determine whether to stop at N=30 or continue recruitment to the newly calculated sample size (up to a maximum of 50 total subjects). If conditional power based on the age effect observed so far is less than 30% then stopping for futility will be recommended.

Based on the results a pilot study of the FreeStyle Navigator™ (Abbott Diabetes Care) performed by DirecNet, a sample size of 30-50 subjects will result in approximately 1,800-3,000 sensor-reference pairs giving a 95% confidence interval for the median relative absolute difference no more than  $\pm 1.0\%$ . With this sample size the half width of the 95% confidence interval for the median difference will be approximately  $\pm 5-6$  mg/dL.

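### The 92% power in section 7.1 belongs to a single test at a fixed N=50; the interim rules in the same section deliver about 82%, or about 86% if futility stopping is not followed

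*Protocol*

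**What the plan says.** Section 7.1 of the protocol takes a standard deviation that "for epinephrine was 306 pg/mL", assumes "a two-tailed test with type I error rate of 5" per cent, and concludes that 50 subjects, 25 per age group, "will give approximately 92% power to detect a mean difference of 300 pg/mL between the two age groups".

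The next two paragraphs of 7.1 describe an interim analysis after 30 subjects:

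- **Re-sizing.** The standard error of the age effect from the first 30 subjects is put into the calculation above "to obtain the sample size necessary to detect a mean difference of 300 pg/mL with 90% power", with a cap of 50.
- **Variance stop.** Recruitment ends at 30, with an unadjusted final test, if 30 subjects give at least 80% "power using the updated variance estimate or if N=50 would only increase this power by" less than 5%.
- **Efficacy.** Otherwise Pocock's "test will be used to determine whether to stop at N=30 or continue recruitment to the newly calculated sample size".
- **Futility.** "If conditional power based on the age effect observed so far is less than 30% then stopping for futility will be recommended".

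These are described as guidelines recommended to the DSMB. No power is given for the design that includes them.

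**The concern.** The 92% describes a trial that always recruits 50 subjects and tests once at 5%. Under the interim rules, a trial that meets the planning assumptions usually ends at 30 subjects. If it continues, it goes to a re-sized N that may be below 50 and is tested at a stricter level than 5%. The re-sizing itself uses the 5% calculation, so it aims at 90% power for a test that will not be run.

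What is at stake is the chance of missing the difference the study was sized for. The DSMB approves the protocol and acts on these rules, and the only power figure in front of it is 92%.

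**Working it through.** **Inputs from section 7.1:** SD 306 pg/mL; difference 300 pg/mL; two-sided 5%; 25 per group at N=50; interim at N=30; variance stop at 80% power or a gain below 5 points; re-sizing to 90% power, capped at 50; Pocock otherwise; futility at conditional power below 30%.

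**Assumptions, because 7.1 does not give them:** 15 per group at the interim; normal data; a two-sample t-test in place of the ANCOVA, as no baseline correlation is stated; no dropout.

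**1. Reproduce the stated figure.** The noncentrality is difference / (SD × √(2/n)).

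- n = 25: 300 / (306 × √(2/25)) = 300 / 86.55 = 3.47 on 48 df, power 92.5%. The stated 92% is right for this test.
- n = 15: 300 / (306 × √(2/15)) = 300 / 111.7 = 2.68 on 28 df, power 73.6%.

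**2. Variance stop.** Power at N=30 reaches 80% when the interim SD is 283 or less. With a true SD of 306, the chance is P(χ² on 28 df ≤ 28 × (283/306)² = 23.95) = 0.32.

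**3. Pocock level.** For looks at 30 and 50 (information 0.6 and 1), the common critical value is 2.161, a nominal p of 0.0307. A single test at that level with N=50 has 88.9% power.

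**4. Re-sizing.** At SD 306 and 5%, 90% power needs 23 per group (90.2%), so N=46. Tested at 0.0307, the same 46 subjects give 85.9%. Reaching 90% at 0.0307 needs 26 per group (90.2%), which is N=52 and above the cap.

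**5. Futility.** With final N=50, conditional power under the observed effect is below 30% when the interim z is below √0.6 × (2.161 − 0.524 × √0.4) = 1.42.

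**6. The rules together.** Simulation of 200,000 trials, applying the rules in the order variance stop, Pocock efficacy, futility, continuation:

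| Path | Share of trials | Contribution to power |
|---|---|---|
| Variance stop at N=30, tested at 5% | 31.7% | 0.317 × 0.829 = 0.263 |
| Pocock efficacy at N=30 | 41.3% | 0.413 |
| Futility at N=30 | 8.8% | 0 |
| Continue to the re-sized N | 18.1% | 0.147 |
| **Total** | | **0.823** |

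About 82% of trials end at N=30 (31.7 + 41.3 + 8.8), and expected N is 33.3. With futility not applied, power is 85.7% and expected N is 34.9. Using normal rather than t formulas, or computing conditional power to N=50, gives 81.4% to 82.9% with futility and up to 86.3% without.

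**7. Type I error.** Simulated with no difference, it is 4.7%, or 5.1% without futility.

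**8. Other true SDs, with futility followed:**

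| SD | Fixed N=50 | Interim rules |
|---|---|---|
| 280 | 96.0% | 86.1% |
| 306 | 92.5% | 82.3% |
| 330 | 88.3% | 78.2% |

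**9. Effect of re-sizing at the Pocock level.** Repeating step 6 with the re-estimated N computed at 0.0307 (400,000 trials) gives about 83% with futility and about 87% without. Expected N is about 34 and 35.

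**The case against.** **The quoted sentence is conditional on 50 subjects and is true.** That stands. A reader might infer that the 92% is miscalculated, but it is not. What is missing is the power of the design that the next paragraphs define. The introduction to Chapter 7 lets the later analysis plan supersede section 7.2 only, so 7.1 would remain as it reads.

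**The rules are recommendations, so futility need not be followed.** This also stands, and it is why two figures are needed. A reader might infer that the chance of missing the effect more than doubles. That needs binding futility (17.7% against 7.5%); with futility not applied it is 14.3% against 7.5%.

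**The sponsor openly accepts 80% power at N=30.** That is fair. A reader might see a contradiction between the 80% stop and the 90% re-sizing target, but a floor for stopping and a target for continuing can coexist. Trials stopped by the variance rule still reject 82.9% of the time, and removing that rule alone leaves overall power at 82.5%.

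**ANCOVA would raise power.** It would. With assumed baseline correlations of 0.3 and 0.5, the interim design gives 84.5% and 88.5%. The fixed design then gives 94.5% and 97.5%, so a gap of 9 to 10 points remains.

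**The clause on a gain below 5%.** A reader might infer that it ends the trial when the trial is weakest. Outside the 80% rule it can act only if the estimated SD exceeds about 1,050 pg/mL, more than three times the planning value, and only if 5% means percentage points. It plays no part in the shortfall.

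**Conclusion.** The point holds as a misstatement of the power of the planned design. Section 7.1 offers 92%. Its own rules, at its own SD and difference, deliver about 82% with futility followed and about 86% without, a shortfall of roughly 10 and 7 points. About 3 points of the larger shortfall come from futility. The rest comes from ending or testing at 30 subjects, the stricter Pocock level, and a re-sized N that can be below 50.

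The absolute figures rest on an SD of 306 being true, equal groups at the interim, and no covariate gain. The gap itself is similar at SDs of 280 and 330.

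A reader might infer that the interim rules inflate the false-positive rate or have to be redesigned. The documents do not support either. Type I error is about 5%, and early stopping is a legitimate trade-off in children undergoing induced hypoglycemia.

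**What to change.** In section 7.1:

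1. Label the 92% as the power of a single 5% test at a fixed N=50.
2. Add the power under the interim rules: about 82% if the futility guideline is followed and about 86% if it is non-binding, with expected N about 33 (about 35 without futility) and the assumptions named.
3. Compute the re-estimated N at the Pocock level that the final test will use. This adds about one point (about 83% and 87%), so the figures in item 2 should be updated if it is adopted. At SD 306 the 90% target would then need 52 subjects, so the text should say that the cap of 50 applies.

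The cost is protocol and DSMB wording and a less favourable stated power. Item 3 makes continued trials slightly larger, but the maximum stays at 50.

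A different boundary, a higher variance-stop threshold or another conditional-power convention is optional. Such changes would recover power but would end fewer trials at 30, and the point does not depend on them.

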### 7.2 Analysis Plan

#### 7.2.1 Counterregulatory Responses during Insulin-induced Hypoglycemia

##### 7.2.1.1 Hormone Concentrations

Boxplots will be used to summarize the distribution of hormone levels separately for the two age groups by glucose level. An analysis of covariance model (ANCOVA) will be fit separately for each hormone with the change from baseline to peak during the subcutaneous insulin infusion test as the dependent variable. The model will include a term for age group (3-<7 vs. 12-<18) with baseline hormone concentration as the covariate.

A repeated measures regression model will also be fit treating each hormone measurement as a separate observation (instead of just using the peak value as above). Either an autoregressive or Toeplitz structure will be used to model the covariance pattern. Residual values will be checked for

918 approximate normality. If the distribution is highly skewed a transformation may be used.  
919 Suspected outliers will either be truncated or excluded.

920  
921 Additional exploratory models will be fit to assess possible associations of counterregulatory  
922 responses with the following covariates:

- 923 • age as continuous
- 924 • HbA1c
- 925 • gender
- 926 • BMI percentile
- 927 • clinical center
- 928 • glycemic indices as measured by the Guardian RT during home use prior to the  
929 subcutaneous insulin infusion test (see section 7.2.2.1)

930  
931 Continuous covariates will be modeled as linear in the dependent variable or divided into categories  
932 if significant non-linearity is detected. The number of hypoglycemic episodes per 24 hours  
933 measured by the Guardian RT will also be categorized as  $<2.0$  vs.  $2.0-<3.0$  vs.  $\geq 3.0$ .

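### Section 7.2.1.1 orders suspected outliers in the hormone models to be truncated or excluded, with no criterion and no limit to assay error, which can make standard errors too small and may ease the N=30 stop

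*Protocol*

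**What the plan says.** Section 7.2.1.1 fits two models to each hormone. The first is an ANCOVA "with the change from baseline to peak during the subcutaneous insulin infusion test as the dependent variable", with terms for age group and baseline concentration. The next paragraph adds a second model: "A repeated measures regression model will also be fit treating each hormone measurement as a separate observation". That second paragraph goes on to the covariance structure and a residual check, then says "If the distribution is highly skewed a transformation may be used", and ends with "Suspected outliers will either be truncated or excluded". The optional verb governs the transformation; the mandatory one governs the outliers.

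Section 7.1 makes the interim at N=30 depend on the first model: "The standard error for the age effect from the ANCOVA model for epinephrine described in section 7.2.1.1 will be calculated using the outcome data". If the updated variance gives at least 80% power at N=30, or if going to N=50 would add less than 5%, recruitment ends and the analysis proceeds with no adjustment for alpha spending.

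The opening of Chapter 7 says that a later analysis plan will supersede section 7.2. That plan has to be final before the study is completed. It is not required before the N=30 look, and section 7.1 is not among the text to be superseded.

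**The concern.** The dependent variable in the ANCOVA is a peak change in hormone level, so an extreme value may be a genuine response and not a faulty measurement. A rule that alters or removes values because they look extreme, chosen after they are seen, does two things. It takes real variation out of the residual variance, so the standard error is too small for the test that follows. It also leaves the analyst to decide which values are suspect and which of two quite different treatments they receive, with nothing requiring that decision to be made without knowledge of age group.

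Two results are at stake. One is the validity of the age comparison. The other is the interim decision, if the rule reaches the epinephrine ANCOVA: a smaller estimated variance makes it easier to stop at 30 subjects and test at full alpha.

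**Working it through.** **Inputs from section 7.1.** SD "for epinephrine was 306 pg/mL"; target difference 300 pg/mL; two-sided 5% test; interim at N=30. Fifteen subjects per age group at the interim is an assumption.

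**The plan's own figure.** The plan states that "a sample size of 50 subjects (25 in each age group) will give approximately 92% power". The standard error is 306 × √(2/25) = 86.6, and 300/86.6 = 3.466. Normal approximation: Φ(3.466 − 1.960) = 93.4%. Noncentral t with 48 df: 92.5%. The stated figure reproduces.

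**Power at N=30 with the planning SD.** 306 × √(2/15) = 111.7, and 300/111.7 = 2.685. Normal: Φ(2.685 − 1.960) = 76.6%. Noncentral t with 28 df: 73.6%. Both are below 80%. N=50 adds about 17 points (93.4 − 76.6, normal). At the planning SD, neither part of the stopping condition is met.

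**SD at which the stop is met.** Normal: 300/(SD × √(2/15)) = 1.960 + 0.842 gives SD = 293, a fall of 4% (293/306 = 0.958). Noncentral t: SD = 283, a fall of 7.5% (283/306 = 0.925).

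**What an outlier rule does to the SD and the test.** The protocol gives neither a distribution nor a cut-off, so both are assumed here. Each case has 4,000 simulated trials with 15 per group, a two-sample t-test without the baseline covariate, true SD 306 (root mean square of the two groups' SDs where spread is proportional) and cut-offs applied to residuals. Mean SD, stop probability (estimated SD at or below 283) and estimated difference come from runs with a true difference of 300. The rejection rate comes from runs with no difference.

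| Data | Rule | Mean SD | Chance of stop | Rejection, no age effect | Estimated difference |
|---|---|---|---|---|---|
| Normal | none | 303 | 33% | 4.9% | 301 |
| Normal | exclude beyond 2 SD | 272 | 60% | 9.9% | 302 |
| Normal | exclude, Tukey fences | 285 | 48% | 7.5% | 301 |
| Normal | truncate at 2 SD | 294 | 41% | 5.7% | 300 |
| Normal | exclude beyond 3 SD | 302 | 33% | 5.0% | 300 |
| Right-skewed, equal spread | none | 285 | 60% | 4.3% | 300 |
| Right-skewed, equal spread | exclude beyond 2 SD | 182 | 96% | 6.7% | 297 |
| Right-skewed, equal spread | truncate at 2 SD | 231 | 81% | 5.2% | 299 |
| Right-skewed, spread proportional to mean (150 vs 450) | none | 283 | 62% | not run | 302 |
| Same | exclude beyond 2 SD | 173 | 97% | not run | 221 |
| Same | truncate at 2 SD | 223 | 83% | not run | 272 |

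A separate run on normal data gave 9.6% at 2 SD and 6.6% at 2.5 SD. The difference between 9.6% and 9.9% is within simulation error: √(0.099 × 0.901/4000) is about 0.5 points.

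The 2 SD rule flags 3.6% of subjects in normal data, or 0.036 × 30 = about one subject in 30. Removing roughly one person is therefore enough to double the error rate. In normal data about half the flagged values are low ones. In the proportional-spread case, 86–95% of flagged values, across the cut-offs tried, lie in the group with the larger response.

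**The case against.** The strongest reply is that section 7.2 is only a framework and outlier criteria are usually set in the analysis plan. That stands as far as the missing criterion goes: a protocol that left outliers to the analysis plan would not be at fault. Here, however, the protocol gives a positive instruction to alter or remove values, and its replacement may come after the interim.

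The second reply is about reach. The outlier sentence closes the repeated-measures paragraph and does not name the ANCOVA, whereas section 7.1 takes its standard error from the ANCOVA. This stands. Applying the rule to the interim model is a fair reading of a shared section, but the text does not say it.

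The third reply is about size. With a 3 SD cut-off on normal data nothing of note happens. Truncation keeps the subject and costs little type I error. Even with no outlier handling, sampling variation alone meets the 80% stop in 33% of normal-data runs. All of this stands, and it means that the harm depends on a choice the protocol does not state.

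A reader might also infer that the rule strips out the high responders and so biases the age difference toward zero, or that the plan itself expects skewed hormone data. The documents support neither. The sentence does not single out high values, the remark on skewness is conditional, and no hormone distribution is given.

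**Conclusion.** The point holds as a defect in a stated rule. Exclusion on suspicion makes the standard error too small. On normal data with 15 per group, type I error rises to about 9.6% at 2 SD and 6.6% at 2.5 SD, and is essentially unchanged at 3 SD; truncation at 2 SD gives 5.7%. These are error rates for a single test, not for the whole interim procedure.

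Attenuation of the age difference is conditional. It appears only when spread is assumed to grow with the response (302 falling to 221 under 2 SD exclusion) and not when spread is equal. That pattern is plausible for a peak hormone change, but it is an assumption.

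The interim consequence is conditional too. If the rule applies to the epinephrine ANCOVA, a fall in estimated SD of 4% (normal) to 7.5% (t) from 306 pg/mL moves N=30 power from 74–77% to 80% and ends recruitment at full alpha. It should not be said that outlier handling will cause such a fall: on normal data, 2 SD exclusion lowers the mean SD to 272, while a 3 SD rule leaves it at 302. The simulations omit the baseline covariate and assume equal groups. The change should be made, and is not one on which the study fails.

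**What to change.** Before the N=30 look, replace the outlier sentence in section 7.2.1.1 with:

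> *All assayed values are kept; a value is removed only for a documented specimen or assay error, judged without reference to age group. If residuals are highly skewed, the final analysis uses log concentrations (log peak with log baseline as covariate) or ranks/normal scores; truncation or exclusion is a labelled sensitivity analysis only.*

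The log is taken of each concentration because the change from baseline can be zero or negative and cannot be logged directly.

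Add to section 7.1 that the interim variance uses all valid values on the raw pg/mL scale. A standard error on a log or rank scale cannot enter a power calculation for a difference of 300 pg/mL.

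The cost is two short edits. The standard error may be larger than after trimming, so the N=30 stop may be met less often, and effects on a log or rank scale need translating back for the reader.
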